Plasticity in the Spinal Cord to Enhance Motor Retraining after Stroke

NCT03645122

July 25, 2024

OBJECTIVE: Noninvasive neuromodulation targeting synapses that link corticospinal neurons onto the final common pathway via spike-timing-dependent mechanisms can alter distal limb motor output on a transient basis, yet these effects appear subject to individual differences. The objective of this study was to investigate how this form of noninvasive neuromodulation interacts with task repetition to influence early learning of force control during hand movements foundational to everyday tasks and susceptible impairment after neurological injury.

DESIGN: Experiments were conducted using a within-subject, repeated-measures design involving separate testing sessions under three counterbalanced conditions that were randomized within a subject and pseudorandomized across subjects: Rest, Sham, and Active. During conditioning stimulation, single-pulse TMS was used to depolarize corticospinal terminals and electrical current as applied to the ulnar nerve to depolarize spinal motor neurons antidromically. Depolarization of corticospinal terminals and spinal motor neurons occurred with hand muscles at rest in the Rest condition. Depolarization of *only* spinal motor neurons occurred immediately after precision grip force was stabilized in the Sham condition. Depolarization of corticospinal terminals and spinal motor neurons occurred immediately after precision grip force was stabilized in the Active condition. In this way, comparisons of PCMS alone, task repetition alone, and PCMS during task repetition was possible. RMSE was measured at baseline and following conditioning stimulation at three separate time points under each condition to quantify force stability.

STATISTICAL ANALYSIS PLAN: A 4 (time point) \times 3 (condition) repeated-measures ANOVA was used to test for differences in RMSE. The Bonferroni test was used to correct for multiple comparisons.

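### Does the objective of how PCMS interacts with task repetition need a factorial interaction test that three conditions cannot give?

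*Combined protocol and SAP*

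**What the plan says.** The document is a single combined text with three parts. The Objective is to "investigate how this form of noninvasive neuromodulation interacts with task repetition to influence early learning of force control".

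The Design is within-subject, "involving separate testing sessions under three counterbalanced conditions":

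- **Rest:** "Depolarization of corticospinal terminals and spinal motor neurons occurred with hand muscles at rest in the Rest condition". This is paired stimulation without the task.
- **Sham:** depolarization of only "spinal motor neurons occurred immediately after precision grip force was stabilized in the Sham condition". This is the task with ulnar nerve stimulation but no TMS.
- **Active:** paired stimulation delivered once grip force has stabilized, so both components are present.

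The Design then gives the purpose of the set: "comparisons of PCMS alone, task repetition alone, and PCMS during task repetition was possible". On the outcome it says: "RMSE was measured at baseline and following conditioning stimulation at three separate time points under each condition".

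The Statistical Analysis Plan has two sentences. A 4 (time point) by 3 (condition) "repeated-measures ANOVA was used to test for differences in RMSE", and "The Bonferroni test was used to correct for multiple comparisons". It does not say which ANOVA term or contrast answers the Objective, how the three post times are combined, or how many comparisons Bonferroni covers. The document states no sample size, standard deviation, effect size or alpha.

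**The concern.** To a statistician, the word interacts suggests a 2 x 2 layout, PCMS yes or no by task yes or no, with non-additivity as the target. Only three of the four cells were run. The missing one is ulnar stimulation only with the hand at rest. Meanwhile the planned ANOVA does have an interaction term, condition x time, which is a different thing.

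A reader could therefore take a significant condition x time effect as proof of synergy, or a null one as proof of additivity. Neither follows. In addition, the contrasts the design does support are not listed as tests, and the Bonferroni divisor is open, so the per-test threshold depends on a choice the SAP does not record. Finally, Sham keeps the ulnar stimulation, so describing it as task repetition alone is loose.

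**Working it through.** There is no planned figure to reproduce, so the check is structural. Cell definitions come from the Design and the model from the SAP. All numerical changes below are assumed illustrations in arbitrary RMSE units.

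**1. What three cells identify.** Write the change from baseline with four parameters (common change, PCMS, task, PCMS x task). The common change is what the missing cell would show.

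- Rest = (1, 1, 0, 0)
- Sham = (1, 0, 1, 0)
- Active = (1, 1, 1, 1)

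The rank is 3 for 4 parameters. Estimable: Active - Sham = PCMS + PCMS x task; Active - Rest = task + PCMS x task; Rest - Sham = PCMS - task. PCMS x task by itself is not estimable. It equals Active - Rest - Sham + c, with c the change in the missing cell. Setting c = 0 assumes both that repeated testing produces no change and that ulnar stimulation at rest has no effect.

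**2. Whether an ANOVA term tests it.** Take changes (Rest, Sham, Active) constant over the three post times, with baseline 0. The time pattern (0, 1, 1, 1) has sum of squares about its mean 0.75² + 3 x 0.25² = 0.75, so the condition x time sum of squares on cell means is 0.75 times the between-condition sum of squares of the changes.

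| Pattern | Changes | Between-condition SS | Condition x time SS | Active - Rest - Sham |
|---|---|---|---|---|
| A | -1, -1, -2 | 0.667 | 0.50 | 0 |
| B | 0, 0, -1 | 0.667 | 0.50 | -1 |
| C | -1, -1, -1 | 0 | 0 | +1 |

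A and B look the same to condition x time but differ in non-additivity (taking c = 0). C gives no condition x time effect although the contrast is +1. The weights (-1, -1, +1) have mean -1/3 and squared length 3, so a share 3 x (1/9) / 3 = 1/9 lies in the time main effect and 8/9 in condition x time. A simulation (assumed n = 20, unit residual SD, 5% level, 4,000 replicates) agrees: condition x time was rejected in 62% of runs under A, which is exactly additive if c = 0, and in 4.6% under C.

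**3. Whether the supported comparisons sit inside the planned model.** For Active - Sham on change from baseline, the condition weights (0, -1, +1) sum to zero and the time weights (-1, 1/3, 1/3, 1/3) sum to zero. The contrast therefore lies wholly in condition x time. The same holds for the other two pairs. So condition x time is the right omnibus term for the comparisons the Design describes.

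**4. The open Bonferroni divisor (alpha 0.05 assumed).**

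- 2 contrasts: 0.05/2 = 0.025
- 3 condition pairs: 0.05/3 = 0.0167
- 2 contrasts at 3 post times: 0.05/6 = 0.0083
- 3 pairs at 3 post times: 0.05/9 = 0.0056
- all pairs of the 12 cells: 12 x 11 / 2 = 66, and 0.05/66 = 0.00076

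For 80% power on one contrast (normal approximation), (z + 0.842)² is 9.51, 10.47, 12.11 and 13.06 for families of 2, 3, 6 and 9. Moving from 3 to 9 costs 13.06/10.47 = 1.25 times the sample size.

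**The case for a change.** The strongest case for a change is that the concern survives a friendly reading. Even if the Objective means only that the combination is compared with each component, the SAP still names no contrast, no handling of post times and no family. The Design says comparisons were possible, which is not the same as specifying a test. The 22-fold spread in threshold (0.0167 / 0.00076) is then real latitude. Nor is c = 0 assured, because RMSE is measured four times per session and repetition alone may shift it.

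All of that is correct as description. Two things limit it. First, the non-additivity argument is aimed at a claim the document does not make: it mentions neither additivity nor synergy and sets no rule for reading condition x time that way. The misreading would be the reader's, and following the plan as written gives no wrong result. Second, the threshold spread is wide only if one admits families the Design does not point to. Its purpose sentence lists three conditions to compare, which leads to three pairs.

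Estimating non-additivity from the three cells would gain little. With c from -1 to +0.5 (assumed), pattern A moves from -1 to +0.5, so the sign depends on the assumption. With equal variances and a between-condition correlation r of 0 to 0.7 (assumed), the variance ratio to a pairwise contrast, (3 - 2r) / (2(1 - r)), runs from 1.5 to 2.7.

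The Sham label is loose, but the same section states exactly what Sham contained, so nobody is misled about the comparison.

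**Conclusion.** No change to the plan follows. Non-additivity of PCMS and task is not identified by Rest, Sham and Active (rank 3 of 4), and no term of the 4 x 3 ANOVA has it as its null. But the Design sets the study up as comparisons among the three conditions, and for those the design and model are adequate: all three pairwise contrasts are estimable, and on change from baseline they lie within condition x time.

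The residue is missing detail in a two-sentence SAP. An analyst would sensibly take the three condition pairs on change averaged over the post times, with a Bonferroni family of 3 (0.0167 per test if alpha is 0.05), and would read Sham as task repetition with ulnar stimulation. The text is in the past tense, so contrasts named now could not be presented as prespecified if the data have already been analysed, and the sample-size multipliers have nothing to act on.

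This conclusion rests on reading interacts in the comparative sense that the Design supports. A report claiming synergy or additivity from condition x time would go beyond both the design and the plan.

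### The 4 × 3 ANOVA omits session (period), so any session-to-session drift in RMSE stays in the error term and costs power

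*Combined protocol and SAP*

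**What the plan says.** The DESIGN paragraph describes separate testing sessions under "three counterbalanced conditions that were randomized within a subject and pseudorandomized across subjects". Every participant therefore has a session 1, 2 and 3, each holding a different condition. On the outcome it says that "RMSE was measured at baseline and following conditioning stimulation at three separate time points under each condition", which gives 4 × 3 = 12 values per participant.

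The conditions differ in how much grip work they contain. Stimulation "occurred with hand muscles at rest in the Rest condition", whereas in Sham it came "immediately after precision grip force was stabilized in the Sham condition", and Active followed the same grip procedure as Sham. The paragraph concludes that "comparisons of PCMS alone, task repetition alone, and PCMS during task repetition was possible".

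The STATISTICAL ANALYSIS PLAN names two factors, time point and condition, and a Bonferroni correction: a 4 × 3 "repeated-measures ANOVA was used to test for differences in RMSE". It gives no session, period or order term. The sample size, the number of participants per order, the session spacing and the set of Bonferroni comparisons are not stated.

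**The concern.** The OBJECTIVE asks how stimulation "interacts with task repetition to influence early learning of force control". When the outcome is a learned skill and the same task is tested in three sessions, performance may well drift from one session to the next. Counterbalancing stops such drift from favouring one condition, but it does not remove the drift from the data. Unless session is modelled, the drift goes into the participant × condition error, the condition test becomes conservative, and a real Active–Sham or Active–Rest difference in level is easier to miss.

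A second issue follows from the unequal grip work. If a Sham or Active session passes on more practice than a Rest session, equal session positions do not guarantee unbiased level comparisons, and a session-number term does not correct this.

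**Working it through.** The plan states no power, sample size or effect size, so there is no planned figure to reproduce.

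**Inputs from the documents:** three sessions, one condition each; counterbalanced order; four RMSE measurements per session; factors time point and condition only.

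**Assumed inputs:** n = 18 (also 12 and 30); α = 0.05; six orders used equally; variances of 1 for participant, 0.5 for session within participant and 0.5 for residual; participant × time variance 0 (also 0.125 and 0.25); an Active effect of 0.6 at all three post times.

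**1. Level drift and the condition effect.** A linear step d per session gives centred shifts of −d, 0 and +d, with sum of squares 2d² per participant. With balanced orders all of it falls in the participant × condition error, which has 2(n − 1) df, so the error mean square rises by 2nd²/[2(n − 1)] = nd²/(n − 1). In units of the session-mean error variance at n = 18:
- d = 0.5 SD: 1 + 18 × 0.25/17 = 1.265; SE × √1.265 = 1.125.
- d = 0.25 SD: 1 + 18 × 0.0625/17 = 1.066; SE × 1.03.

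**2. Level drift and condition × time.** A shift common to all four time points of a session cancels from post minus baseline, so nothing is lost.

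**3. Changing gain and condition × time.** Take change as the mean of the three post values minus baseline. Its error variance is 0.5 + 0.5/3 = 0.667. For a gain that changes by 0.4 per session (0.8, 0.4, 0), inflation is 1 + (18 × 0.16/17)/0.667 = 1.254, SE × 1.12. For a step of 0.2 it is 1.064, SE × 1.03.

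**4. Power by simulation** (20,000 replicates at n = 18; 10,000 at n = 12 and 30). Planned error df at n = 18 are 34 for condition and 102 for condition × time; with the session terms they are 32 and 96.

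| Scenario | Test | n | Planned | With session terms |
|---|---|---|---|---|
| Level step 0.5 SD | Condition | 12 | 16% | 25% |
| Level step 0.5 SD | Condition | 18 | 26% | 37% |
| Level step 0.5 SD | Condition | 30 | 47% | 59% |
| Level step 0.25 SD | Condition | 18 | 35% | 38% |
| Level step 0.5 SD | Condition × time | 18 | 41% | 41% |
| Gain 0.8, 0.4, 0 | Condition × time | 12 | 21% | 26% |
| Gain 0.8, 0.4, 0 | Condition × time | 18 | 35% | 41% |
| Gain 0.8, 0.4, 0 | Condition × time | 30 | 61% | 67% |
| Half that gain | Condition × time | 18 | 39% | 41% |

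Type I error at n = 18 is 2.6% planned against 5.2% with session (level step 0.5 SD), and 3.5% against 5.1% (gain 0.8, 0.4, 0). For the Active–Sham change from baseline, with Bonferroni over an assumed three contrasts, power is 28% against 38%, and 37% against 39% at half the gain. With no order effect the extra terms cost at most 0.3 points at n = 18 and 0.5 at n = 12.

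A separate simulation with other assumptions (residual SD 1, participant × condition SD 0.5, n = 18) and larger drifts gave condition power of 68% against 85% at a shift of 0.5 per session, and 20% against 84% at 1.0. The direction is the same; the size depends on the assumed drift.

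**5. Unequal carry-over.** Suppose each earlier grip-task session (Sham or Active) shifts later level by p. Every condition has mean session position 2.0, but the mean number of earlier grip-task sessions differs:
- All six orders: Rest (0+0+1+1+2+2)/6 = 1; Sham and Active each (0+0+0+1+1+1)/6 = 1/2. Rest is shifted by p/2 against both others; Active–Sham is not shifted.
- Three cyclic orders (R-S-A, S-A-R, A-R-S): Rest 1, Sham 1/3, Active 2/3. Rest–Sham is shifted by 2p/3 and Active–Sham by p/3.

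Least squares with participant, session and condition leaves these shifts unchanged. Adding the preceding condition with six orders takes a one-session carry-over from 0.333p to 0, and a cumulative one from 0.50p to 0.375p, with contrast variance × 1.25. With cyclic orders the variance rises fivefold and the cumulative shifts stay at 2p/3 and p/3.

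**The case against.** The strongest reply is about relevance. Condition × time is the test nearest the objective, and a level drift leaves it alone. The condition main effect averages in the pre-stimulation baseline, so an effect of 0.6 after stimulation becomes 0.6 × 3/4 = 0.45 there; it is a weak measure of stimulation with or without a session term. Harm to condition × time needs a changing within-session gain, which the documents do not show, and the 6-point loss assumes that gain is exhausted by session 3. With milder drift or gain change the losses are 2 to 3 points. The planned test is conservative under balance, and a completed study could only be re-analysed. All of this stands and keeps the point minor.

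It does not remove the point. The size of the drift is unknown, and the added terms cost almost nothing if it is absent. Two considerations also run the other way. If order counts are unequal, a session shift biases the condition estimates. If practice acts proportionally on RMSE, it changes the within-session gain and so reaches condition × time.

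On carry-over, the reply is that RMSE is tested in Rest sessions too, so p represents only the extra practice in Sham and Active and may be small. That is fair. It limits the size of p, not the direction of the shifts.

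**Conclusion.** The concern holds and is minor. The design assigns session order and the stated analysis ignores it, so a level drift would reduce power for the condition effect and for between-condition comparisons of level. In the assumed cases at n = 18 the loss is about 3 points at a step of 0.25 SD (35% against 38%) and 11 at 0.5 SD (26% against 37%). Condition × time loses nothing from a pure level drift, and about 2 to 6 points if gain declines as assumed. The absence of bias rests on balanced orders and on practice that does not depend on the preceding condition. The second proviso may fail, mainly for level comparisons with Rest; with three cyclic orders Active–Sham is exposed as well. A pure level carry-over still cancels from change from baseline. None of this invalidates the planned ANOVA.

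**What to change.** - Keep the planned error structure (participant, participant × session, participant × time) and add session (1, 2, 3) and session × time as fixed effects beside condition, time and condition × time. Session alone does not help condition × time.
- In mixed-model form, use random effects for participant, session within participant and participant × time. Do not drop participant × time: the OBJECTIVE itself notes of the stimulation effects, "yet these effects appear subject to individual differences". Under the assumed gain change, dropping it cuts condition × time power to 25% (variance 0.125) or 14% (variance 0.25), with type I error of 1.6% or 0.5%; keeping it gives 41% and 40% with the session terms.
- Report which orders were used and the number analysed in each.
- Add a sensitivity analysis of the level comparisons that includes the preceding condition (the session term covers session 1, which has none), with change from baseline shown beside it. State its limits: with six orders it only reduces a cumulative carry-over; with three cyclic orders it is too imprecise to rely on and leaves a cumulative carry-over untouched.

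Cost: no new data. At n = 18, two error df for condition (34 to 32) and six for condition × time (102 to 96). The sensitivity analysis raises contrast variance by 25% with six orders. Session order was assigned by design and should be on record. The document is written in the past tense, so if the study is complete, report this beside the planned ANOVA and label it as a re-analysis.

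### Bonferroni is valid as planned; Holm over the same fixed family is an optional improvement with a modest gain for second and later contrasts

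*Combined protocol and SAP*

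**What the plan says.** All references are to the combined protocol and SAP.

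- **STATISTICAL ANALYSIS PLAN.** The main analysis crosses four time points with three conditions: "repeated-measures ANOVA was used to test for differences in RMSE". Multiplicity is covered by one further sentence, "The Bonferroni test was used to correct for multiple comparisons". No stepwise method is mentioned.
- **DESIGN.** Each subject is tested under "three counterbalanced conditions that were randomized within a subject and pseudorandomized across subjects: Rest, Sham, and Active". On the outcome, "RMSE was measured at baseline and following conditioning stimulation at three separate time points under each condition to quantify force stability". The section adds that "comparisons of PCMS alone, task repetition alone, and PCMS during task repetition was possible".
- **OBJECTIVE.** The aim is to learn how the neuromodulation "interacts with task repetition to influence early learning of force control".

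The document does not state the contrasts that Bonferroni covers or how many there are. Nor does it give the familywise alpha, sample size, SD or expected effect.

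**The concern.** Single-step Bonferroni holds every contrast to alpha/m, however many of the others have already been rejected. Holm relaxes the threshold after each rejection at no cost to the nominal familywise level. Where several contrasts are truly non-zero, Bonferroni therefore gives up some power that the same error bound would allow.

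This design has a natural use for a second rejection. Rest delivers the paired stimulation with the hand muscles at rest, Sham has the grip task with spinal motor neurons alone depolarized, and Active combines task and paired stimulation. To show that the combination differs from each component, Active must differ from Sham and also from Rest. The plan does not state that as a success criterion, but it is the reading that the DESIGN section invites, and it takes two rejections from one family.

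What is at stake is power for second and later contrasts. The validity of the planned analysis is not in question.

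**Working it through.** The plan has no power or error figure to reproduce. The check has a general part, which needs no assumed figure, and an illustrative part.

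**1. Holm contains Bonferroni.** Order the m p-values as p(1) ≤ … ≤ p(m). Bonferroni rejects contrast i if p(i) ≤ α/m. Holm rejects in order while p(i) ≤ α/(m − i + 1) and stops at the first failure. Since α/(m − i + 1) ≥ α/m at every step, any p-value that passes Bonferroni is reached and passed by Holm. The first thresholds are both α/m, so the chance of at least one rejection is identical.

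**2. Same strong bound.** Let m₀ contrasts be truly null. The first true null that Holm could reject comes no later than step m − m₀ + 1, where the threshold is at most α/m₀. The chance that any of m₀ true nulls falls below α/m₀ is at most m₀ × α/m₀ = α, under any dependence.

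**3. Thresholds at an assumed α = 0.05.** The family is not stated, so a range is shown.

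| m | Bonferroni, every contrast | Holm, second step | Holm, last step |
|---|---|---|---|
| 3 | 0.01667 | 0.0250 | 0.05 |
| 9 | 0.00556 | 0.00625 | 0.05 |
| 12 | 0.00417 | 0.00455 | 0.05 |
| 18 | 0.00278 | 0.00294 | 0.05 |
| 66 | 0.00076 | 0.00077 | 0.05 |

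**4. Size of the gain, three condition contrasts.** Assumptions, none from the document: two-sided 0.05, residual SD 1 in each condition, only Active different, paired t-tests, simulated trials. Anchor for Bonferroni at N=18 and 0.9 SD: d_z = 0.9/√2 = 0.64, noncentrality = 0.9/√2 × √18 = 2.70, 17 degrees of freedom. The noncentral t distribution at 0.05/3 gives 53.1%, in line with the simulation.

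Active versus Sham, N=18, effect varied:

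| True difference | Bonferroni | Holm | Gain (points) |
|---|---|---|---|
| 0.3 SD | 5.9% | 6.3% | 0.4 |
| 0.5 SD | 15.7% | 16.9% | 1.2 |
| 0.9 SD | 53.0% | 56.7% | 3.7 |
| 1.5 SD | 95.7% | 97.1% | 1.4 |

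Over the same four effects, the gain for rejecting both Active contrasts is about 1 to 7 points. At 0.9 SD, with N varied:

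| N | Both rejected, Bonferroni | Holm | Gain (points) |
|---|---|---|---|
| 12 | 15.9% | 21.2% | 5.3 |
| 18 | 35.7% | 42.9% | 7.2 |
| 24 | 55.2% | 62.6% | 7.4 |
| 30 | 70.9% | 77.3% | 6.4 |

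At N=18 and 0.9 SD, the chance of any rejection is 70.6% under both methods.

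**5. Other families.** A separate simulation used all 12 cells, a shift of 0.8 SD in Active at the three later times, and correlation 0.6. At N=20, average power per non-null contrast under Bonferroni and Holm was:

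- m=3: 78.8% and 82.6%
- m=9 (changes from baseline within condition): 78.9% and 81.0%
- m=12 (condition pairs at each time): 75.7% and 80.5%
- m=18 (time pairs within condition): 70.8% and 71.8%
- m=66 (all cell pairs): 51.8% and 55.5%

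Over N = 12, 20 and 30 the gain ran from about 0.4 to 4.9 points. No Bonferroni rejection was lost in any of the 30 scenarios.

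**6. Where the gain vanishes.** With one non-null contrast among nine within-condition changes (N=18, 0.9 SD), power is 35.7% under Bonferroni and 35.8% under Holm. Among three condition contrasts this case cannot arise, because one difference implies at least two.

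**7. A further step for three condition contrasts.** Once one of the three equalities is false, at most one of the other two can be true. After the smallest p-value passes α/3, the other two may therefore each be tested at α. At N=18 and 0.9 SD, the Bonferroni, Holm and constrained figures are 53, 57 and 62% for Active versus Sham, and 36, 43 and 54% for both Active contrasts.

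**8. Cost in realised error.** Suppose only Rest = Sham is true and Active is very far from both. Bonferroni tests the true null at 0.05/3 = 1.7%. Holm reaches it at its last step, at 5.0%. Simulation gave about 1.6% and 5.0%, and the constrained version also gave 5.0%. With all conditions equal, all three methods gave about 4.5%.

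**The case against.** The strongest reply is that this is a preference. Bonferroni is valid, simple and familiar. It gives simultaneous confidence intervals that match its tests, and its realised error is lower under partial nulls. All of that stands, and it is why the point is optional. What remains is that, for the test decisions alone, Holm is never worse at the same nominal bound.

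A second reply is that the benefit may no longer be available. The text is in the past tense throughout, for example "Experiments were conducted using a within-subject, repeated-measures design". If the analysis has been run, Holm cannot restore confirmatory power. This stands and limits the recommendation.

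A third reply is that the gain depends on the assumed effect. At N=18, of the four effects tried, 0.9 SD shows Holm at its best, and the gain is well under 1 point at 0.3 SD. This also stands, and is why a range is given.

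Three stronger inferences are tempting and not supported:

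- **That Bonferroni is an error here.** Nothing in the plan suggests that it fails to control familywise error over the family it covers.
- **That the sponsor should adopt a particular list of contrasts.** The document names none, and 3, 9, 12, 18 or 66 are all conceivable after this ANOVA. Imposing a list could change the contrasts, which is a different proposal.
- **That pairs would be tested unadjusted after a significant F test.** The plan proposes no such thing.

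**Conclusion.** The point holds as an optional improvement. That Holm keeps the error bound and every Bonferroni rejection follows from the two procedures and needs no assumption about this trial, except that the family is the same and was fixed before results were seen. The document does not show that this condition is met. The unstated alpha and contrasts are a separate gap, which Holm does not fill.

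The size is modest and conditional on assumed values. For three condition contrasts at N=18, it is roughly 0.4 to 4 points for Active versus Sham and 1 to 7 points for both Active contrasts. A reader might infer from the larger figures that the plan gives up a substantial amount of power. The document gives no sample size or effect from which to conclude that, and the gain is near zero when only one contrast is non-null.

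**What to change.** **If the analysis has not been run:** replace the multiplicity sentence with one saying that the contrasts Bonferroni was to cover, listed before results are seen, are tested by the Holm step-down procedure at the stated two-sided familywise alpha. If that list is the three condition contrasts, the sentence may add that, once the smallest p-value passes alpha/3, the other two are each tested at alpha.

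**If the analysis has been run:** keep Bonferroni as the planned result and report Holm only as a labelled post hoc sensitivity analysis.

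**Cost:** one sentence, with no new data and no change to the ANOVA, the outcome or the contrasts. Simple matching simultaneous confidence intervals are lost, and realised error under partial nulls moves closer to alpha. If such intervals matter more to the sponsor than the extra power, keeping Bonferroni is a reasonable choice.
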